13.4.3 Analysis of the Safety Endpoints

The overall rates of device and procedure related Major Adverse Events (MAEs) through 30 days post procedure, (primary safety endpoint) as well as the components and secondary safety endpoints, will be calculated, with 95% confidence intervals.

13.4.4 Key Secondary Endpoints (through 1 year)

The following secondary efficacy endpoints will be tested in a hierarchical order after the primary endpoints have passed (i.e., achieved statistical significance at pre-specified alpha level), in order to address multiple testing and control family-wise error. When one of the endpoints does not achieve statistical significance at two-sided alpha = 0.05

PROTOCOL NUMBER: 2017-05

in favor of the Device group, no further testing of subsequent endpoints will be conducted.

Mitral Regurgitation (MR)

Superiority test of Device group versus Control group via the chi-square statistic, for the difference in the prevalence of MR \leq 1+ at one year, with a two-sided alpha of 0.05. The null (H_0) and alternative (H_A) hypotheses are:

 H_0 : $P_{CardB} - P_{Control} = 0$

 H_A : $P_{CardB} - P_{Control} \neq 0$.

 P_{CardB} and $P_{Control}$ are the prevalence of MR \leq 1+ at one year in the Device and Control groups, respectively.

New York Health Association (NYHA)

Superiority test of Device group versus Control group via the Chi-square statistic, for the difference in the proportion of subjects with NYHA class I/II at one year, with a twosided alpha of 0.05. The null (H_0) and alternative (H_A) hypotheses are:

 H_0 : $P_{CardB} - P_{Control} = 0$

H_A: P_{CardB} - P_{Control} ≠ 0.

P_{CardB} and P_{Control} are the proportion of subjects with NYHA I/II at one year in the Device and Control groups, respectively. Fisher's Exact Test will be performed if assumptions for the Chi-square test are not met.

Kansas City Cardiomyopathy Questionnaire (KCCQ)

The KCCQ scores at baseline and 1 year will be quantified as continuous variables ranging from 0 to 100 and the difference between the two time points will be calculated. This difference (i.e., delta) will be analyzed with T statistic with a two-sided alpha of 0.05. The null (H_0) and alternative (H_A) hypotheses are:

 H_0 : $\Delta_{CardB} = \Delta_{Control}$

HA: ∆CardB ≠ ∆Control

PROTOCOL NUMBER: 2017-05

 Δ_{CardB} and $\Delta_{Control}$ represent mean deltas for the Device and Control groups, respectively.

Six Minute Walk Test (6MWT)

The 6MWT distance at baseline and 1 year will be quantified as continuous variables measured in meters and the difference between the two time points will be calculated. This difference in distance (i.e., delta) will be analyzed with T statistic with a two-sided alpha of 0.05. The null (H_0) and alternative (H_A) hypotheses are:

 H_0 : $\Delta_{CardB} = \Delta_{Control}$

 H_A : $\Delta_{CardB} \neq \Delta_{Control}$

 Δ_{CardB} and $\Delta_{Control}$ represent mean deltas for the Device and Control groups, respectively.

36-Item Short Form Survey (SF-36)

SF-36 score at baseline and 1 year will be quantified as continuous variables ranging from 0 to 100 and the difference between the two time points will be calculated. This difference (i.e., delta) will be analyzed with T statistic with a two-sided alpha of 0.05. The null (H_0) and alternative (H_A) hypotheses are:

 H_0 : $\Delta_{CardB} = \Delta_{Control}$

 H_A : $\Delta_{CardB} \neq \Delta_{Control}$

 Δ_{CardB} and $\Delta_{Control}$ represent mean deltas for the Device and Control groups, respectively.

Heart Failure Hospitalizations

The number of heart failure hospitalizations between day 0 and day 365 post procedure will be quantified as recurrent events and analyzed with a survival analysis intensity model.³⁰ The null (H₀) and alternative (H_A) hypotheses are:

 H_0 : HR = 1

 H_A : $HR \neq 1$

HR represents hazard rates for Device group relative to Control group, respectively. Two-sided alpha of 0.05 will be used.

Cardiovascular Mortality

PROTOCOL NUMBER: 2017-05

Cardiovascular mortality rate up to 365 days will be compared between the Device and Control groups using time-to-event analysis and log-rank test. The null (H₀) and alternative (H_A) hypotheses are:

 $H_0: HR = 1$

H_A: HR ≠ 1

HR represents hazard rates for Device group relative to Control group, respectively. Two-sided alpha of 0.05 will be used.

All-Cause Mortality

All-cause mortality rate up to 365 days will be compared between the Device and Control groups using time-to-event analysis and log-rank test. The null (H₀) and alternative (H_A) hypotheses are:

 H_0 : HR = 1

H_Δ: HR ≠ 1

HR represents hazard rates for Device group relative to Control group, respectively. Two-sided alpha of 0.05 will be used.

13.4.5 Analysis of Additional Secondary Endpoints

Analysis of additional secondary endpoints will be performed using descriptive statistics. Details of these analyses will be provided in the SAP.

13.4.6 Adverse Events Analyses

Adverse events (AE) will be summarized by treatment for the FAS population and mITT and AEs will be summarized by severity and relatedness. Serious AEs will be presented in a listing.

13.4.7 Adherence and Retention Analyses

Adherence to the protocol requirements and patient dispositions will be summarized by study treatment.

13.4.8 Demographics, Baseline Characteristics, Laboratory and Medication, Medical History, and Procedure Characteristics and Concomitant Medication

Intervention groups should be compared on baseline and procedure characteristics, including demographics and laboratory measurements, using descriptive statistics, as well as change from baseline where appropriate.

13.4.9 Interim Analyses and Safety Monitoring

An interim analysis will be performed for the purpose of sample size re-estimation and will be described in the SAP.

Periodic safety analyses are to be performed during the trial as required by the appropriate regulatory authorities, and under the review the DSMB. Details will be provided in the DSMB charter.

13.5 Determination of Sample Size

Co-primary endpoint I

Using PASS software and a test for two independent proportions 375 enrolled patients give us >99% power to detect a difference between the groups using the following assumptions:

- 1. Proportion in control arm who meet the criteria for MR reduction (MR \leq 2+) is 10%.
- 2. Proportion in treatment arm who meet the criteria for MR reduction (MR \leq 2+) is 70%.
- 3. A two-sided significance level (alpha) of 0.05.
- 4. A 2:1 treatment allocation ratio between Edwards Cardioband System (Device group) and control group.
- 5. Data will be available for 60% of the randomized patients (accounting for mortality and lost to follow-up).

Co-primary endpoint II

Assuming up to 20% dropout, a total of 375 enrolled patients will ensure at least 300 patients with evaluable data. Based on 5,000 trial simulations using SAS software (version 9.4), it is estimated that 300 evaluable patients will provide 87% power to

detect superiority of treatment vs. control using the Finkelstein-Schoenfeld test and the following assumptions:

- 1. All-cause mortality of 20% within the first year in both groups (Control and Device).
- 2. Cardiovascular mortality of 15% within the first year in both groups (Control and Device).
- 3. Number of heart failure hospitalizations within the first year:
 - a. 60% of the patients in the Control and 70% in the Device group will not have HF hospitalization.
 - b. 10% of the patients in the Control group and 10% of the patients in the Device group will have one HF hospitalization.
 - c. 10% of the patients in the Control group and 5% in the Device group will have two HF hospitalizations.
 - d. 10% of the patients in the Control group and 5% in the Device group will have three HF hospitalizations.
 - e. 5% of the patients in the Control group and 5% in the Device group will have four HF hospitalizations.
 - f. 5% of the patients in the Control group and 5% in the Device group will have five or more HF hospitalizations.
- 4. Improvement in 6-minute walk test at one year vs. baseline:
 - 10% of the patients in the Control group and 50% of the patients in the Device group will have an improvement in 6 minutes walking distance of 40 meters or more compared to their baseline result.
- 5. Improvement in KCCQ score at one year vs. baseline:
 - 10% of the patients in the Control group and 50% of the patients in the Device group will have an improvement in KCCQ score of 10 points or more compared to their baseline result.
- 6. A two-sided significance level (alpha) of 0.05.
- 7. A 2:1 treatment allocation ratio between Device group and Control group.

All event rates above are conservative estimates based on previous experience with the Edwards Cardioband System, as well as on data on patients with functional mitral regurgitation who underwent catheter based treatment with the CE marked CARILLON® device (Cardiac Dimensions, Kirkland, WA) or the MitraClip® device (Abbott Vascular, Santa Clara, CA) from two registries (Sentinel¹ and ACCESS-EU²) and three studies (EVEREST II^{3,4}, TRAMI⁵⁻⁷, TITAN⁸).

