- 4. A 2:1 treatment allocation ratio between Edwards Cardioband System (Device group) and Control group.

Co-primary endpoint II

Assuming up to 20% attrition, a total of 375 enrolled patients will ensure at least 300 patients with evaluable data. Based on 10,000 trial simulations using SAS software (version 9.4), it is estimated that 300 evaluable patients will provide > 90% power to detect superiority of treatment vs. control using the Finkelstein-Schoenfeld test and the following assumptions:

- 1. All-cause mortality of 20% within the first year in both groups (Control and Device).
- 2. Cardiovascular mortality of 15% within the first year in both groups (Control and Device).
- 3. Number of heart failure hospitalizations within the first year:
 - a. 60% of the patients in the Control and 70% in the Device group will not have HF hospitalization.
 - b. 10% of the patients in the Control group and 10% of the patients in the Device group will have one HF hospitalization.
 - c. 10% of the patients in the Control group and 5% in the

[figure not shown]
Device group will have two HF hospitalizations.

- d. 10% of the patients in the Control group and 5% in the Device group will have three HF hospitalizations.
- e. 5% of the patients in the Control group and 5% in the Device group will have four HF hospitalizations.
- f. 5% of the patients in the Control group and 5% in the Device group will have five or more HF hospitalizations.
- 4. Improvement in 6-minute walk test at one year vs. baseline: 10% of the patients in the Control group and 50% of the patients in the Device group will have an improvement in 6 minute walking distance of 40 meters or more compared to their baseline result.
- 5. Improvement in KCCQ score at one year vs. baseline:
 10% of the patients in the Control group and 50% of the patients in the Device group will have an improvement in KCCQ score of 10 points or more compared to their baseline result.
- 6. A two-sided significance level (alpha) of 0.05.
- 7. A 2:1 treatment allocation ratio between the Device group and Control group.

The sample size will be re-estimated when at least 40% of patients have undergone 1 year primary efficacy endpoint assessment.

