If the conditional power is <90% then the sample size will be reestimated to include the number of patients necessary to achieve 90% conditional power. The group allocation ratio of 2:1 (Device vs. Control) will be retained. Increase in the sample size will be at the discretion of the Sponsor and pursuant to FDA approval. Additional scenarios (such as 80% power) may be requested.

All event rates above are conservative estimates based on previous experience with the Edwards Cardioband System, as well as on data on patients with functional mitral regurgitation who underwent catheter based treatment with the CE marked CARILLON® device (Cardiac Dimensions, Kirkland, WA) or the MitraClip® device (Abbott Vascular, Santa Clara, CA) from two registries (Sentinel¹ and ACCESS-EU²) and three studies (EVEREST II³,4, TRAMI⁵-7, TITAN®).

Clinical Events	A group of individuals with pertinent expertise that reviews clinical study
Committee (CEC)	endpoints to determine whether the endpoints meet protocol-specified
	criteria.
Data Safety	An independent data monitoring committee that may be established by
Monitoring Board:	the sponsor to assess, at intervals, the progress of a clinical trial, the
	safety data, and the critical efficacy endpoints, and to recommend to the
	sponsor whether to continue, modify, or stop a trial.

Table 1: Schedule of Study Visits and Patient Assessments

Test/ Assessment	Screening/ Baseline	Random -ization	Pre-Index Procedure- Edwards Cardioband System (Device group only; timing: per local institutional standard of care)	Index Procedure- Edwards Cardioband System (Device group only)	Post- Edwards Cardioband System Procedure, Pre- Discharge (Device group only)	30 Day F/U (±7 days)	180 Day F/U (± 14 days)	1 Year F/U (±45 days)	2 Year F/U (± 60 days)	3, 4, 5 Year F/U (± 60 days)
Study Visit No.	1	2	3	4	5	6	7	8	9	10, 11, 12
Study Consent	X									
Medical Hx/	Х					X	Х	Х	Х	Х
NYHA Class										
STS Score	Х									
Cardiovascular	Х			Х	Х	Х	Х	Х	Х	X
Medications										
Targeted	Х					Х	Х	Х	Х	Х
Physical Exam										
12-Lead ECG	Х				X	Х	Х	Х		
Transthoracic	Х				Х	Х	X	X	Х	Х
Echo (TTE)										
Transesophageal	Х			Х						
Echo (TEE)	X									
Cardiac CT	X									
Imaging Randomization		X								
Pregnancy Test	X ¹	^	X							
(for females of	^-		Χ							
childbearing										
potential only)										
potential only)	 	 								

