13.4.2 Analysis of the Primary Endpoints (Efficacy)

The co-primary endpoints will be analyzed in a hierarchical order where endpoint I must meet statistical significance in order to proceed to endpoint II. This approach does not require any adjustment for multiplicity.

Co-primary endpoint I

The proportion of patients who meet the criteria for reduction of mitral regurgitation $(MR \le 2+)$ at one year follow-up.

The comparison of co-primary endpoint I between Device and Control groups will be performed using a Chi-Square-test for two independent proportions.

Co-primary endpoint II

Conditional on the first co-primary endpoint meeting statistical significance, co-primary endpoint II will be analyzed using the non-parametric method described by Finkelstein and Schoenfeld. Briefly, each patient pair is compared in descending order of the endpoints until one member of the pair shows superiority. As specified above, these endpoints are:

- 1. Time to all-cause death within the first year
- 2. Number of heart failure hospitalizations within the first year
- 3. Improvement of 6-Minute Walk Test at one year vs. baseline (≥ 40 meters improvement)
- 4. Improvement in Kansas City Cardiomyopathy Questionnaire (KCCQ) score at one year vs. baseline (≥10 point improvement).

The specifics of the procedure will be provided in greater detail within the statistical analysis plan (SAP).

The Finkelstein-Schoenfeld method starts by a comparative outcome assessment for all patient pairs. While the example comparison given in the table below shows a Device patient being compared to a Control patient it should be noted that a pairwise comparison is made for every patient versus every other patient.

Comparison of each potential patient pair	How Event is
(e.g. 1 from Device group and 1 from Control group)	Assessed
Step 1	
If 1 or both patients die due to all-cause	
Patient in Device group dies first due to all-cause	Favors Control
Patient in Control group dies first due to all-cause	Favors Device
Both patients die on the same day due to all-cause	Go to Step 2
If neither of the patients die due to all-cause	Go to Step 2

Comparison of each potential patient pair	How Event is
(e.g. 1 from Device group and 1 from Control group)	Assessed
Step 2	
If no ranking yet available	
Patient in Device group had more hospitalizations** for HF	Favors Control
Patient in Control group had more hospitalizations** for HF	Favors Device

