### 3.3 **Primary Efficacy Endpoints (1 Year)**

- a. Co-primary efficacy endpoint 1: Prevalence of MR  $\leq$  2+ at 1 year
- b. Co-primary efficacy endpoint 2:
  - i. Time to all-cause death
  - ii. Number of heart failure hospitalizations
  - iii. Improvement in Six Minute Walk Test (6MWT) relative to baseline (≥ 40 meters improvement)
  - iv. Improvement in Kansas City Cardiomyopathy Questionnaire (KCCQ) relative to baseline (≥ 10 points improvement)

Co-primary efficacy endpoint 1 must meet statistical significance in order to proceed to co-primary efficacy endpoints 2. This approach does not require any adjustment for multiplicity. The co-primary efficacy endpoints were chosen in order to capture the ability of the Edwards Cardioband System to effectively reduce MR (co-primary endpoint 1) and improve clinical outcomes (co-primary endpoints 2).

THIS DOCUMENT CONTAINS CONFIDENTIAL AND PROPRIETARY INFORMATION OF EDWARDS LIFESCIENCES, LLC. IT MUST NOT BE REPRODUCED OR DISCLOSED TO THIRD PARTIES WITHOUT PRIOR WRITTEN PERMISSION OF EDWARDS LIFESCIENCES, LLC. (This template is required by DOC

	2017-05 Sta	tistical Analysis Plan I			1.0   7/16/20	19
E	Revision Date: Febr	uary 28, 2019	Rev		For Use Only by Affiliates of Edwards Lifesciences	Page 6 of 18
Edwards	Title	Statistical Analysis Plan	for	ACTIVE	2017-05	

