### 8. STATISTICAL ANALYSIS OF STUDY ENDPOINTS

### 8.1 Co-Primary Hypothesis 1

H0:  $P_{Device}(T=1) - P_{Control}(T=1) = 0$ H1:  $P_{Device}(T=1) - P_{Control}(T=1) \neq 0$ 

where

H₀	= Null hypothesis
H1	= Alternative hypothesis
P Device	= Proportion of patients in the Device group with $MR \le 2+$ at 1 year
P Control	= Proportion of patients in the Control group with MR $\leq$ 2+ at 1 year
Т	= Time (years)

The co-primary hypothesis 1 tests the superiority in reducing MR of the Device group relative to the Control group via Chi-Square test for two independent proportions with two-sided alpha = .05. Co-primary efficacy endpoint 1 must meet statistical significance in order to proceed to co-primary efficacy endpoints 2. This approach does not require any adjustment for multiplicity.

### 8.2 Co-Primary Hypothesis 2

 $H_0$ : None of the four co-primary endpoints 2 are improved by treatment  $H_1$ : At least one of the four co-primary endpoints 2 is improved by treatment

- i. Time to all-cause death within the first year
- ii. Number of heart failure hospitalizations within the first year
- iii. Improvement in Six Minute Walk Test (6MWT) at 1 year relative to baseline (≥ 40 meters improvement)
- iv. Improvement in Kansas City Cardiomyopathy Questionnaire (KCCQ) at 1 year relative to baseline (≥ 10 points improvement)

The co-primary hypothesis 2 tests the superiority of the Device group relative to the Control group for the hierarchical sequence of the four co-primary endpoints 2 via the Finkelstein-Schoenfeld test (Finkelstein and Schoenfeld, 1999). The Finkelstein-Schoenfeld test is a generalization of the Gehan Wilcoxon test. Each patient pair is compared in descending order of the endpoints until one member of the pair shows superiority. While the example comparison given in the table below shows a Device patient being compared to a Control patient it should be noted that a pairwise comparison is made for every patient in Device group versus every patient in Control group.

THIS DOCUMENT CONTAINS CONFIDENTIAL AND PROPRIETARY INFORMATION OF EDWARDS LIFESCIENCES, LLC. IT MUST NOT BE REPRODUCED OR DISCLOSED TO THIRD PARTIES WITHOUT PRIOR WRITTEN PERMISSION OF EDWARDS LIFESCIENCES, LLC. (This template is required by DOC.))

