### 8.10 Interim Analysis

The sample size will be re-estimated when at least 40% of patients have undergone 1 year primary efficacy endpoint assessment. This re-estimated will be conducted through simulation in the following steps:

- a. Data from the sample that has completed the study will be treated as fixed and retained in each simulation
- b. Data from patients who have not completed the study will be simulated, under the assumption that the observed data in the sample from (a) is representative of the true population value for the four co-primary endpoints 2 (see section 3.2.2).
- c. Data from (a) and (b) will be combined and the Finkelstein-Schoenfeld methodology will be conducted and resulting probability will be calculated.
- d. Steps (a) through (c) will be repeated 10,000 times.
- e. The proportion of the 10,000 iterations for which the resulting probability from the Finkelstein-Schoenfeld test is less than .05, will be taken as the estimate of conditional power.

If the conditional power is < 90% than the sample size will be re-estimated to include the number of patients necessary to achieve 90% conditional power. The group allocation ratio of 2:1 (Device vs Control) will be retained. Increase in the sample size will be at the discretion of the sponsor and pursuant to FDA approval. Additional scenarios (e.g., conditional power is < 80%) may be requested.

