### 8.11 Determination of Sample Size

Co-primary endpoint 1

Using PASS software and a test for two independent proportions 375 enrolled patients give us >99% power to detect a difference between the groups using the following assumptions:

- 1. Proportion in control arm who meet the criteria for MR reduction (MR  $\leq$  2+) is 10%.
- 2. Proportion in treatment arm who meet the criteria for MR reduction (MR  $\leq$  2+) is 70%.
- 3. A two-sided significance level (alpha) of 0.05.
- 4. A 2:1 treatment allocation ratio between Edwards Cardioband System (Device group) and control group.
- 5. Data will be available for 60% of the randomized patients (accounting for mortality and lost to follow-up).

#### Co-primary endpoint 2

Assuming up to 20% dropout, a total of 375 enrolled patients will ensure at least 300 patients with evaluable data. Based on 5,000 trial simulations using SAS software (version 9.4), it is estimated that 300 evaluable patients will provide 87% power to detect superiority of treatment vs. control using the Finkelstein-Schoenfeld test and the following assumptions:

- 1. All-cause mortality of 20% within the first year in both groups (Control and Device).
- 2. Cardiovascular mortality of 15% within the first year in both groups (Control and Device).
- 3. Number of heart failure hospitalizations within the first year:
  - a. 60% of the patients in the Control and 70% in the Device group will not have HF hospitalization.

THIS DOCUMENT CONTAINS CONFIDENTIAL AND PROPRIETARY INFORMATION OF EDWARDS LIFESCIENCES, LLC. IT MUST NOT BE REPRODUCED OR DISCLOSED TO THIRD PARTIES WITHOUT PRIOR WRITTEN PERMISSION OF EDWARDS LIFESCIENCES, LLC. (This template is required by DOC

E	Revision Date: February 28, 2019		Rev		For Use Only by Affiliates of Edwards Lifesciences	Page 17 of 18
Edwards	Title	Statistical Analysis Plan for ACTIVE 2017-05				

- b. 10% of the patients in the Control group and 10% of the patients in the Device group will have one HF hospitalization.
- c. 10% of the patients in the Control group and 5% in the Device group will have two HF hospitalizations.
- d. 10% of the patients in the Control group and 5% in the Device group will have three HF hospitalizations.
- e. 5% of the patients in the Control group and 5% in the Device group will have four HF hospitalizations.
- f. 5% of the patients in the Control group and 5% in the Device group will have five or more HF hospitalizations.

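### The planned power of co-primary endpoint II is given as above 90% in the synopsis and as 87% in Protocol 13.5 and SAP 8.11, on the same listed assumptions

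*Protocol*

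**What the plan says.** Three places state the power of co-primary II:

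- Protocol synopsis (Sample Size & Endpoint Analysis), 10,000 simulations: "it is estimated that 300 evaluable patients will provide > 90% power to detect superiority of treatment vs. control".
- Protocol 13.5, 5,000 simulations: "it is estimated that 300 evaluable patients will provide 87% power".
- SAP 8.11, 5,000 simulations: "it is estimated that 300 evaluable patients will provide 87% power to detect superiority of treatment vs. control".

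Each starts from 375 enrolled patients less 20%, and each lists the same mortality, hospitalization, walk-test and KCCQ rates, alpha and allocation. SAP section 10, which lists departures from the protocol, does not mention the power.

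The documents also disagree on the first step of the hierarchy that was simulated. The pairwise table in Protocol 13.4.2 begins "If 1 or both patients die due to all-cause". SAP 3.3 lists "Time to all-cause death" and the text of SAP 8.2 lists "Time to all-cause death within the first year". Step 1 of SAP Table 1, however, is written for cardiovascular death, and the SAP's pairwise rules treat non-cardiovascular deaths as censored.

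On the secondaries, Protocol 5.4 and SAP 3.6 head the eight key endpoints *Powered*, while the synopsis heads the same list *Hierarchical Testing*. Protocol 13.5 and SAP 8.11 calculate power only for the two co-primaries.

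**The concern.** One set of inputs, one test and one sample size should give one power, apart from simulation error. Co-primary II is the main clinical test, and its power is the main justification for 375 patients, because co-primary I exceeds 99% power with far fewer. A reader who compares the synopsis with the body of the protocol cannot tell which figure the design rests on, or which unlisted assumptions separate the two.

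The heading *Powered* raises a smaller problem of the same kind: it implies a calculation that neither document contains.

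**Working it through.** **Inputs (the same in the synopsis, Protocol 13.5 and SAP 8.11).** One-year mortality 20% all-cause and 15% cardiovascular in both arms. HF hospitalizations 0/1/2/3/4/5+: Control 60/10/10/10/5/5%, Device 70/10/5/5/5/5%. Responders on each of the walk test and KCCQ: Control 10%, Device 50%. Two-sided 0.05, allocation 2:1.

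**1. Sample size.** 375 × 0.80 = 300 evaluable, or 200 Device and 100 Control. This reproduces.

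**2. Simulation error.** SE at 87% with 5,000 runs: sqrt(0.87 × 0.13 / 5000) = 0.0048. At 90% with 10,000 runs: sqrt(0.90 × 0.10 / 10000) = 0.0030. SE of the difference: sqrt(0.0048² + 0.0030²) = 0.0056. The smallest gap is 0.03 / 0.0056 = 5.3 SE. If 87% was rounded from 87.5%, it is still 0.025 / 0.0056, or about 4.5 SE.

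**3. Power from the listed inputs.** I simulated the SAP 8.2 statistic, T/√V with V = m(N−m)/(N(N−1)) × ΣU², over all pairs. My assumptions are uniform event and loss times over the year, *5 or more* counted as 5, and a latent-normal correlation rho between the walk test and KCCQ, with components otherwise independent. Runs of 10,000 have an SE of 0.2–0.3 points. The null rejection rate was 5.2%.

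| Scenario (200:100 unless stated) | Power |
|---|---|
| All-cause step 1, complete data, independent | 93.5%; 93.9% with hospitalizations counted over the full year |
| Same, rho 0.4 | 89.8% |
| Same, rho 0.65 | 86.7% and 87.2% (two runs) |
| Same, walk test and KCCQ identical | 73.6% |
| Independent, 10% missing, each instrument separately | 88.1% |
| Independent, 10% missing, both together | 86.0% (3,000 runs) |
| 250:125 with 20% lost during the year, independent | 87.8% |
| CV-death step 1, complete data, independent | 96.1% |
| CV-death step 1, complete data, rho 0.65 | 90.8% |

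The listed inputs alone reproduce the synopsis figure and do not reproduce 87%. Several plausible but unstated inputs do give about 87%.

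**4. Why the dependence matters.** Among Device–Control pairs, 0.8 × 0.8 = 0.64 have both patients alive.

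- HF hospitalization favours Device in 0.3275 of these and Control in 0.2275 (net 0.10), and ties in 0.445.
- At the walk test, Device wins 0.5 × 0.9 = 0.45 and loses 0.5 × 0.1 = 0.05 (net 0.40), with 0.50 tied.
- An independent KCCQ adds 0.50 × 0.40 = 0.20, for a net of 0.60. An identical KCCQ adds nothing.

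The net advantage over all pairs is 0.64 × (0.10 + 0.445 × 0.60) = 0.235 if independent, and 0.64 × (0.10 + 0.445 × 0.40) = 0.178 if identical. The ratio is 0.76. The simulated mean test statistics, 3.35 and 2.54, have the same ratio.

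**5. Secondaries.** With equal mortality in both arms (20% and 15%), the two mortality tests reject only at alpha: 5% two-sided, about 2.5% in favour of Device.

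For HF hospitalization, the means are 1.05 (Control) and 0.80 (Device), with variances 2.3475 and 2.16. At 200:100, SE(log ratio) = sqrt(2.16/(200 × 0.64) + 2.3475/(100 × 1.1025)) = 0.195. Then |log(0.80/1.05)| / 0.195 = 1.39, and power is about 29%. At 250:125 it is about 34%. This is a rate-ratio approximation with robust variance, not the planned Andersen-Gill model.

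**The case against.** The two dedicated sample-size sections agree on 87%, and only the synopsis differs. All three give the same enrolment, and no analysis or decision rule depends on the planning power. This stands. It makes the matter an inconsistency to reconcile, not a flaw in the test. It does not explain how two figures arise from one list.

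The power conflict may also follow from the step-1 conflict. At rho 0.65, all-cause death gives about 87% and cardiovascular death 90.8%, so one set of unlisted inputs could produce both printed figures. This is possible but not documented: both protocol locations name all-cause death.

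A reader might infer more than the documents support:

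- **That 87%, or the figure above 90%, is wrong.** Neither is shown to be. Both are reachable, depending on inputs that are not stated.
- **That a design at 87% starts below the plan's own 90% criterion.** The synopsis says "If the conditional power is <90% then the sample size will be reestimated" and SAP 8.10 says "If the conditional power is < 90% than the sample size will be re-estimated". That conditional power is computed from interim data held fixed and from rates observed at the interim. Planning power does not enter it.
- **That the trial is short of a definite number of patients.** Any conversion presupposes which figure is right and under which assumptions.
- **That co-primary I has the same defect**, because the synopsis cites 20% attrition and Protocol 13.5 cites 60% data availability. Mortality of 20% plus dropout of 20% leaves 60%, and power exceeds 99% either way.

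On the secondaries, it is fair to say that *Powered* states no number, that the text beneath the heading concerns hierarchical testing, and that Protocol 13.5 calls its rates conservative, so equal mortality need not be the expected result. The HF hospitalization figure also depends on the variance estimator, which the plan does not name. With model-based variance, nominal rejection is about 55%, but at a type I error of about 21%.

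**Conclusion.** The documents give two incompatible planning powers for co-primary II on identical listed assumptions. The gap is at least 3 points, about 5.3 Monte Carlo standard errors. The listed inputs with complete data and independent components give about 93–94%, consistent with the synopsis. Reaching 87% needs something unlisted: a latent correlation near 0.65, about 10% missing functional data, or losses simulated within the 375. These results rest on the timing, top-category and correlation assumptions stated above. Step 1 moves power by about 3 to 4 points at rho 0.65 (90.8% against 86.7% and 87.2%), so it may be part of the cause.

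This is an internal inconsistency in a stated power, not an arithmetic error. It does not invalidate the test or the sample size.

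As a secondary labelling point, *Powered* has no calculation behind it. For the two mortality endpoints it does not fit the only mortality rates the documents give.

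**What to change.** 1. Reconcile step 1 of the hierarchy across Protocol 13.4.2, SAP 3.3, SAP 8.2 and SAP Table 1, including the SAP rule on non-cardiovascular deaths. This needs settling in its own right and must come first, because it changes the simulated power.
2. Re-run the simulation once under the agreed hierarchy. State one power figure, with one number of runs, in the synopsis, Protocol 13.5 and SAP 8.11.
3. State with it the assumed walk-test–KCCQ dependence and the missingness, plus event timing if losses are simulated. A short sensitivity range would help but is good practice, not the correction itself.
4. In Protocol 5.4 and SAP 3.6, replace *Powered* with the synopsis label *Hierarchical Testing*, and note that the mortality endpoints are not powered under the planning rates. If an HF hospitalization power is quoted, label it as an approximation.

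The cost is one simulation re-run and a few wording changes. The correction needs no extra patients and no change to the test. The stated power may become less favourable than the synopsis now suggests.
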